# 11.5 Objectives and End Points Summary

Primary Objective	Primary Endpoint	Outcome Measures		
Compare efficacy between 12 and 24 weeks treatment (sofosbuvir/velpatasvir) in patients with genotype 3 HCV and cirrhosis who have detectable virus after 2 weeks therapy	SVR12 defined as HCV RNA below limit of quantification up to 15 iu/mL - 12 weeks (up to 16 weeks) after treatment discontinuation	
 
Proportion of patients in 12 week arm achieving SVR12
 
Proportion of patients in 24 week arm achieving SVR24
 
		
Secondary Objective	Secondary Endpoints	Outcome Measures		
	
 
Study treatment discontinuation
 
Serious adverse events
 
Quality of life questionnaire at treatment end
 
Quality of life questionnaire at 3 months post-treatment
 
	Proportion of patients in 12 and 24 week arm developing any of listed secondary endpoints  Quality of life score at the end of treatment and at 3 months post treatment, and change in scores over 3 months, for patients in 12 and 24 week treatment arm		

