# Treatment week 12 (study window +/- 7 days) – for arm A (12 weeks) – end of treatment

Record the following between screening visit and end of treatment:

- Concomitant medications review
- Any adverse events/ serious adverse events
- Any treatment discontinuation (of Sofosbuvir/velpatasvir)
- Any missed doses of treatment reported investigators will perform pill count and review returned empty bottles

If participants have left over medication, at the discretion of the study doctor they can complete the remainder tablets, but the end of treatment visit must take place within 7 days of completing medication.

Perform blood samples - FBC, U&Es, creatinine, LFTs, albumin, HCV viral load

Document contraception advice and currently used method (if applicable).

Obtain quality of life questionnaire (SF36) at end of treatment – this does not have to be at the same time as the other visit procedures as long as it is obtained within the visit window

Other procedures or examination performed, as deemed appropriate by investigator, should be recorded in medical notes.

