Perform blood samples - FBC, U&Es, creatinine, LFTs, albumin, optional HCV viral load

Document contraception advice and currently used method (if applicable) – required up to 30 days after last dose of study drug.

Other procedures or examination performed, as deemed appropriate by investigator, should be recorded in medical notes.

End of study - treatment week 24 (+ 28 days) for arm A (12 weeks) or treatment week 36 (+ 28 days) for arm B (24 weeks)

Record the following since the last study visit

Any serious adverse events

Perform blood samples - FBC, U&Es, creatinine, LFTs, albumin, HCV viral load

Obtain quality of life questionnaire (SF36) at end of treatment – this does not have to be at the same time as the other visit procedures as long as it is obtained within the visit window

Other procedures or examination performed, as deemed appropriate by investigator, should be recorded in medical notes.

Study team notifies participant's usual clinician that participant has reached trial endpoints, and returns them to the usual care pathway.

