# 15.19 Assessment of compliance

Compliance will be monitored via pill counting and checking returned empty bottles during study visits. Missed pills will be documented in CRF. Investigators will reiterate dosing schedule and the importance of compliance for efficacy. Participants are considered lost to follow up if there is no end of study visit at post treatment week 12+4 weeks.

There is no provision for supplying additional IMPs which are lost or damaged during the trial. Participants should continue on the study but doses missed due to insufficient drug supply should be recorded as missed doses. Investigators can dispense the next due prescription early to cover for lost or damaged medication. According to local pharmacy policy, if surplus/ replacement medication is available (for example if another patient withdraws from treatment), this can be supplied as IMP for a study participant, provided the medication has not been dispensed from pharmacy, and the usual storage and packaging requirements are complied with.

Any study IMP which is dispensed and unused by the participant will be recalled and destroyed in the site pharmacy. For participants who withdraw during study treatment, they may be eligible to continue treatment on the NHS programme according to their usual clinician's judgement and local Trust guidelines.

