# 19.11 Procedure(s) to account for missing or spurious data

To reduce missing data on the primary outcome, SVR12 will be defined as HCV RNA <15iu/mL from 12 to 16 weeks after end of treatment. This widens the window when SVR12 can be reported. A negative HCV RNA at any point after 12 weeks post-treatment is clinically considered to be a sustained virological cure. Negative HCV RNA at less than 12 weeks post-treatment will be considered non-SVR12.

Non SVR12 will be differentiated by true viral relapse or missing data due to lost to follow up, to allow per-protocol analysis.

Given data is time point specific, data outside of the defined window cannot be carried forward to replace missing data.

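### As written, the SVR12 rule scores a first negative HCV RNA after post-treatment week 16 as non-SVR12 although Section 19.11 calls it a cure; the final visit runs on a different clock, and Section 11.5 names SVR24 for Arm B

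*Protocol*

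**What the plan says.** **Endpoint.** Sections 11.1, 11.3.1 and 19.5, and the endpoint column of the table in 11.5, all give SVR12, measured 12 weeks (up to 16) after end of treatment, for both arms. The outcome-measure column of the same row in 11.5 gives SVR12 for the 12-week arm but, for Arm B, "Proportion of patients in 24 week arm achieving SVR24".

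**Scoring (Section 19.11).** "SVR12 will be defined as HCV RNA <15iu/mL from 12 to 16 weeks after end of treatment". On the clinical meaning of a late result: "A negative HCV RNA at any point after 12 weeks post-treatment is clinically considered to be a sustained virological cure". On results outside the window: "data outside of the defined window cannot be carried forward to replace missing data". A negative before week 12 is explicitly scored non-SVR12. On the make-up of the failures: "Non SVR12 will be differentiated by true viral relapse or missing data due to lost to follow up".

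**Loss to follow-up (Section 15.19).** "Participants are considered lost to follow up if there is no end of study visit at post treatment week 12+4 weeks".

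**Timing of the final visit.** Section 13.8.3 places it at treatment week 24 (Arm A) or 36 (Arm B), plus up to 28 days. Section 11.6 labels those visits post-treatment week 12. At the end-of-treatment visit, in either arm, "If participants have left over medication, at the discretion of the study doctor they can complete the remainder tablets".

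**Withdrawn participants (Sections 13.8.4, 13.9, 13.10).** Their virological outcome may be collected from the usual clinician, and they may continue sofosbuvir/velpatasvir or take another regimen outside the study.

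**The concern.** Section 19.11 sets out to reduce missing primary-outcome data, and its clinical statement of cure has no upper time limit. Its analysis rule does have one, and the section does not say what happens to a participant who is tested late and is negative. Following the text leads to failure. The error runs one way within an arm: a late positive is non-SVR12 under any rule, so the upper limit can only turn cures into failures.

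The same endpoint is exposed at the lower limit. The endpoint runs from end of treatment, whereas the final-visit window in 13.8.3 runs from treatment start. When the last dose slips, a visit inside the permitted window can be too early for SVR12, and no repeat test is provided for.

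The SVR24 entry matters because 11.5 is the summary of objectives and endpoints, and on its face it sets two different primary measures against each other.

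With 30 participants per arm, one misclassified cure moves that arm's SVR by 1/30 = 3.3 percentage points. The drug cost per successful treatment in Section 19.13 would carry the same misclassification.

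**Working it through.** **1. A first negative at post-treatment week 18 (illustrative), followed through the text.**
- Section 19.11, clinical sentence: beyond 12 weeks and negative, so a cure.
- Section 19.11, definition: 18 lies outside 12 to 16, so it is not an SVR12 result.
- Section 19.11, out-of-window rule: it may not stand in for the missing window result.
- Section 15.19: with no end-of-study visit by week 12 + 4 = 16, the participant is lost to follow-up.
- Section 19.11: missing data through loss to follow-up is one of the two kinds of non-SVR12.
- Result: a cure clinically, non-SVR12 in the analysis.

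**2. The two clocks.** Assume, for illustration, a last dose 7 days late.
- Arm A: last dose at week 13; earliest permitted final visit at week 24; 24 − 13 = 11 weeks post-treatment.
- Arm B: last dose at week 25; earliest permitted final visit at week 36; 36 − 25 = 11 weeks.
- Both visits satisfy 13.8.3, yet a negative at either is explicitly non-SVR12 under 19.11.
- The last permitted day is 15 weeks post-treatment (28 − 13, or 40 − 25), so three of the four window weeks remain valid.

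**3. SVR24.** Arm B's last visit is treatment week 36, which is post-treatment week 12, plus 28 days at most. No post-treatment week-24 sample is scheduled, so SVR24 could not be measured.

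**4. The plan's own sample size.** Inputs from Section 19.1: 65% against 95%, 80% power, 95% confidence (taken as two-sided alpha 0.05), 30 per arm planned. Unpooled normal formula: (1.960 + 0.842)² × (0.65 × 0.35 + 0.95 × 0.05) / 0.30² = 23.98, so 24 per arm. The stated minimum reproduces, and nothing in this point changes it.

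**5. Sensitivity of power.** Method: exact enumeration of the uncorrected chi-square test (Section 19.5 names chi-square), 30 per arm. The baseline of 65% against 95% gives 88.0%. The number of misclassified cures is an assumption; k cures lower an arm's SVR by k/30.

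| Cures misclassified | All in Arm B | That number in each arm | All in Arm A |
|---|---|---|---|
| 1 | 65.0 v 91.7: 73.9% | 61.7 v 91.7: 82.0% | 61.7 v 95.0: 92.6% |
| 2 | 65.0 v 88.3: 58.4% | 58.3 v 88.3: 77.5% | 58.3 v 95.0: 95.7% |
| 3 | 65.0 v 85.0: 43.5% | 55.0 v 85.0: 73.7% | 55.0 v 95.0: 97.7% |

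The Arm A column is not a gain. The apparent difference is inflated from 30 points to 33.3, 36.7 and 40.0.

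Equal numbers in each arm keep the difference at 30 points; equal shares of cures do not. By the pooled normal approximation (baseline 84.6%), losing 5% of cures in both arms gives 61.8% against 90.3% and power 74.6%. Losing 10% gives 58.5% against 85.5% and power 65.1%.

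**The case against.** **The late case is inferred.** Only a negative before week 12 is expressly scored as failure. A reader might infer that the protocol says the same of late negatives. It does not: that outcome follows from joining 19.11 to 15.19. The language of carrying values forward fits an early result better than a late one, and the cure sentence can be read simply as the reason for extending the window to 16 weeks. This stands as a limit on how firmly the point can be put. It does not remove the point, because the out-of-window sentence covers all data outside the window and no other sentence rescues a late negative.

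**A fixed window is a legitimate choice, consistently stated.** Agreed. The fault is that the rule departs from the section's own unlimited statement of cure.

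**The final visit is already tied to post-treatment week 12.** Sections 11.6 and 15.19 do this, and the window is one-sided, so most of it stays valid after a short delay. The risk is therefore narrow, and the 7 days above is only an illustration. It remains that 13.8.3 permits a visit that 19.11 must score as failure.

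**Bias against Arm B.** A reader might infer that the longer course makes Arm B the main loser. The protocol does not support this: post-treatment follow-up is 12 weeks with the same 28-day allowance in both arms, and no rate or direction of late sampling is given. Nor does anything show that usual-clinician results often miss the window, since the withdrawal sections ask for the outcome at 12 weeks or 3 months. Section 19.2 expects few withdrawals.

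**SVR24 is a drafting slip.** Very probably, and the arms would not in practice be measured on different endpoints. It still contradicts the rest of the protocol in the primary-outcome row.

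**Conclusion.** The point holds as an inconsistency in how the primary endpoint is scored. Followed as written, Sections 19.11 and 15.19 together make a first negative after post-treatment week 16 a failure that 19.11 itself calls a cure. Section 13.8.3 allows a final visit that can fall before week 12 when the last dose is late. Section 11.5 misnames the Arm B measure.

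The size in this trial cannot be derived from the protocol. Each misclassified cure costs its arm 3.3 points. The power figures rest on assumed counts of 1 to 3 and on the design rates of 65% and 95%, and the effect on the comparison depends wholly on which arm is affected: a loss of power if the cures are in Arm B or in both arms, an exaggerated difference if they are in Arm A. The Arm B-only figures should not be quoted alone. The sample size calculation is untouched.

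**What to change.** Amend the wording so that, in both arms:
- SVR12 is determined from the first HCV RNA test at least 84 days after the actual last dose.
- If there is no result in the 12 to 16 week window, a later negative counts as SVR12, provided there is no earlier positive post-treatment result at or after week 12 and no further HCV treatment after the allocated course.
- Weeks 12 to 16 remain the target visit window.
- The final-visit window in 13.8.3 is stated from the date of last dose.
- SVR24 in 11.5 becomes SVR12.

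Both provisos in the second item are needed. Sections 13.9 and 13.10 allow off-study treatment after withdrawal while the outcome is still collected, so an open-ended rule could credit a negative that other treatment produced, or one that follows a positive test. The sentence in 15.19 on loss to follow-up should be aligned with the new rule.

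The cost is wording only; sample size and treatment are unchanged. The small downside is that a few outcomes will be read after week 16.

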#### 19.12 Other statistical considerations.

NA

#### 19.13 Economic evaluation

This study will not formally evaluate cost effectiveness and cost increment per QALY of the two treatment durations, but will evaluate treatment costs based on drug costs alone per successful treatment (SVR12)

# 20.0 Data Handling & Record Keeping

#### 20.1 Confidentiality

The Principal Investigator has a responsibility to ensure that participant anonymity is protected and maintained. They must also ensure that their identities are protected from any unauthorised parties. Information with regards to study participants will be kept confidential and managed in accordance with the Data Protection Act, NHS Caldicott Guardian, The Research Governance Framework for Health and Social Care and Research Ethics Committee Approval. All trial data will be stored in line with the Medicines for Human Use (Clinical Trials) Amended Regulations 2006 and the Data Protection Act and archived in line with the Medicines for Human Use (Clinical Trials) and all subsequent amendments as defined in the JRMO SOP 20 Archiving.

The Chief Investigator and the study team will adhere to these parameters to ensure that the Participant's identity is protected at every stage of their participation within the study. To ensure this is done accordingly, at time of consent each participant will be allocated a unique screening number by either the PI or a member of the study team before undergoing any screening procedures.

The trial will be conducted in compliance with the requirements of the Data Protection Act 1998. All investigators and trial site staff must comply with the requirements of the Data Protection Act 1998 with regards to the collection, storage, processing and disclosure of personal information and will uphold the Act's core principles.

#### 20.2 Data Custodian Details

The Chief Investigator, [name], Blizard Institute, Queen Mary University of London, is the 'Custodian' of the research data. The study will not collect identifiable information. Unique study identifiers will be used for study documents. A participant ID log will be kept in the Investigator Site File with the Principle Investigator. For purposes of monitoring and audit, original source files containing identifiable data may be inspected by third parties (i.e. the Sponsor or regulatory bodies, and not any other organisation or commercial company). Participants will sign consent to permit access to identifiable data for such purposes. Identifiable data will not leave the study site.

Any publication relating to the study will contain no identifiable data. Research data will be kept for 20 years in accordance to the Sponsor's policy.

# 20.3 Pseudononymisation

The study will use identifiers for participants consisting of ABC-00, where the first three letters are abbreviated for the study site, and the number will be successive participants screened at the site. These details will be used on CRFs and for study correspondence leaving the study site, such as with the Sponsor.

# 20.4 Transferring/Transporting Data

Data containing identifiable information will not be stored on any portable device. Data transferred between sites will contain pseudoanonymised identifiers only. Electronic transfer of data must be in accordance with the UK Data Protection Act 1998.

#### 20.5 Data collection tools and source document identification

Data reported on the CRF/eCRF will be derived from source documents. Researchers delegated with the completion and return of eCRF are responsible for the accuracy of completed data.

Data will be entered at each site on an electronic CRF (eCRF) onto a web-based database. Any data collected via CRF/eCRF for the study belongs to the study Sponsor. The Sponsor will not have access to source data, except during monitoring or audit, but will have access to the anonymous data entered into the database.

#### 20.6 Source Data

Source data is defined as all information in original records of clinical findings, observations and other trial activities necessary for the reconstruction and evaluation of the study. These may contain identifiable information and will be stored in confidential conditions and will not leave the study site. Depending on the site they may be paper medical notes or electronic health records. Their maintenance and storage will be in accordance to the site NHS Trust guideline or policy. A trial monitor may inspect the source data. A source data list will be provided to each site as part of the Investigator Site File to aid consistent monitoring.

Note participants will complete a set of Quality of Life questionnaires, which will be completed in paper form by participants, and transcribed by the study team onto eCRF. ECRF data will be processed using licensed Health Outcome Scoring Software to generate summary scores for each participant during data analysis. These summary scores will be statistically analysed as detailed in the SAP.

#### 20.7 Case Report Form

CRF will be entered electronically onto a trial web-based database, direct from source documents, by investigators/ study nurse.

Paper CRFs will be available in case of technical failures.

# 20.8 Data handling and record keeping

CRFs will be electronically stored and managed by an authorised database (Discovere) which is hosted on a secure served Cerner, a system commissioned by the Sponsor for the secure and confidential handling of data. The system will comply with the requirements and processes specified in SOP 38. It will enable quality control of data (drop down, or fixed range variables, in preference to free text where possible), audit trail, and secure data back up.

Training of staff on the use of eCRF and the data management system will be documented.

# 20.9 Access to Data, Source Data and Documents

Direct access will be granted to authorised representatives from the Sponsor, host institution and the regulatory authorities to permit trial-related monitoring, audits and inspections.

Only members of the health care team directly related to the care of the participant will have access to the participant's medical records.

# 21.0 Archiving

During the course of research, all records are the responsibility of the Chief Investigator and must be kept in secure conditions. When the research trial is complete, it is a requirement of the Research Governance Framework and Trust Policy that the records are kept for a further 20 years.

Site files from other sites must be archived for 20 years at the originating site external site and cannot be stored at the BH Modern Records Centre or within QMUL.

Destruction of essential documents will require authorisation from the Sponsor.

Following submission of the end of study report, the Sponsor will authorise archiving. The sites will archive their Investigator's Site Files. The trial database which contains the eCRF will be archived securely within the system server.

# 22.0 Monitoring, Audit and Inspection

# 22.1 Monitoring

A Trial Monitoring Plan will be developed and agreed by the Sponsor and Chief investigator based on the sponsors trial risk assessment, this will include on site monitoring. Monitoring procedures are detailed in the Trial Monitoring Plan.

# 22.2 Auditing

Sponsor retains the right to Audit any trial, trial site or central facility. In addition, any part of the trial may be inspected by the regulatory bodies and funders where applicable.

# 22.3 Notification of Serious Breaches to GCP and/or the protocol

The Site Principal investigator is responsible for reporting any serious breaches to the sponsor (JRMO) within 24 hours.

The Chief Investigator is responsible for reporting any serious breaches to the sponsor (JRMO) within 24 hours.

The sponsor will work with the CI to investigate any potential breach and notify and report to the MHRA (as applicable) within 7 working days of becoming aware of the serious breach.

A serious breach is a breach likely to affect to a significant degree:

- the safety or physical or mental integrity of the trial participants
- the scientific value of the study

If the above should occur, the sponsor will be notified immediately.

The sponsor will notify the licensing authority in writing of any serious breach of

- the conditions and principles of GCP in connection with the study
- the trial protocol

within 7 days of being aware of the breach

#### 22.4 Compliance

The CI will ensure that the trial is conducted in compliance with the principles outlined in the Medicines for Human Use (Clinical Trials) Regulations 2004 (SI 2004/1031), and any subsequent amendments of the clinical trial regulations, current Research Governance Framework, GCP guidelines, the World Medical Association Declaration of Helsinki (1996), the Sponsor's SOPs, and other regulatory requirements as amended.

#### 22.5 Non-Compliance

Planned deviations or waivers to the protocol are not allowed under the UK regulations on Clinical Trials. Unintentional deviations must be adequately documented and reported to the CI and Sponsor.

Non-compliances may be captured from a variety of different sources including monitoring visits, CRFs, communications and updates. The sponsor will maintain a log of the non-compliances to ascertain if there are any trends developing which need to be escalated.

CI and the coordinating team should assess the non-compliances and action a timeframe in which they need to be dealt with. This assessment should include the need to escalate to the sponsor. Any event with the potential to affect participant safety or data integrity should be reported to the sponsor within 24 hours of the Coordinating team becoming aware.

Where applicable corrective and preventative actions APA should be assigned. Each action will be given a different timeframe dependent on the severity. If the actions are not dealt with accordingly, the Sponsor will agree an appropriate action, including an on-site audit.

